## 6.7. DATA SOURCES

We will simultaneously use various information sources

A) Database created for the register of ProHEPiC-19.

The data will be centralized in an internal centralized data warehouse from the Catalan Health Institute. After data collection and curation, the data is ready to be analyzed to (1) validate the accuracy on demographic, clinical, social, and psychological data of professionals; (2) register SARS-CoV-2 antibodies; (3) results in RT-PCR test.

B) Primary care electronic health records (e-Cap) contain demographic data and clinical variables: health conditions (ICD-10 codes) and diagnostic date, medication prescribed, comorbidities, lab test results (including RT-PCR).

C) Case Report Form (Teleform) specific for the study, which will include a specific identifier for the patient and the serological and immunological tests' information. This information will be shared among the various sources of information about the study employing individual, anonymized participants' identification. Immunological data will be collected to understand the vaccine's protection and the relationship between immune response and reinfection.

## 6.8 STATISTICAL ANALYSIS

Data collection: The data will be exported to the statistical packages used in the study. The people that meet eligibility criteria will be identified and included in the study database. A comprehensive cleaning of the data will be conducted to eliminate inconsistencies, duplicates and treatment indications inconsistent with the diagnosis and analysis of missing data will also be conducted. Additionally, a longitudinal validation of diagnostics and medicines will be carried out.

### 6.8.1 STATISTIC TO MEET PRIMARY AIM: TO CONSOLIDATE A PROSPECTIVE COHORT OF HEALTH CARE WORKERS (HCW) TO GENERATE EPIDEMIOLOGICAL AND CLINICAL HIGH-QUALITY DATA.

A descriptive analysis of the participants will be performed using the number and percentage for categorical variables, and mean and standard deviation or median and quartiles 1 and 3 for quantitative variables. Frequency and percentage of followed-up patients and dropouts will be updated at each timepoint. Profiles of dropouts and visited people will be assessed using the appropriate statistical test in order to prevent potential biases due to drop out. Cohorts will be compared at each time point in terms of sociodemographic, epidemiological, clinical, and immunological information available. To analyze this, an exploratory bivariate analysis will be performed using the tests of Chi Square, ANOVA, Kruskall-Wallis, depending on the application conditions assumptions.

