**Secondary:**

1. To determine the kinetics of SARS-CoV-2 antibodies and cellular immune response in early, mid, and long periods of immunization.
2. To assess the relation between clinical variables and initial RT-PCR results with the interindividual differences in the immune response in early, mid, and long periods of immunization.
3. To analyze differentially expressed cytokines as biomarkers of disease progression in early, mid, and long periods of immunization.

**Methods and analysis:** Longitudinal, dynamic, prospective cohort study with a 12-month follow-up, which is being conducted in 4 primary-care centres and one hospital of Northern Metropolitana Nord of Barcelona (Spain). For now, the study consists of 1350 participants divided into 2 cohorts: 1) Healthy-Exposed HCWs: 675 not infected by SARS-CoV-2 (RT-PCR with a negative result and negative SARS-CoV-2 antibodies at baseline) and 2) Infected HCWs: 675 symptomatic participants (those with new persistent cough, temperature  $\geq 37.5^{\circ}\text{C}$ , anosmia, or ageusia or other compatible symptoms with COVID-19) or asymptomatic participants diagnosed by positive RT-PCR test and/or SARS-CoV-2 antibodies (IgM, IgG at baseline). Primary outcomes include: humoral and cellular immune response, quantitative antibodies to SARS-CoV-2, SARS-CoV-2 antibody levels related to progression phenotype, clinical spectrum of SARS-CoV-2, symptomatology, demographics and other variables that may be predictive of immune response.

**Follow-up:** baseline, 15 days, 1, 3, 6, 9 and 12 months.

**Findings to date:** Current literature has shown that the immune response is maintained for a minimum of 2 months. Nevertheless little is known about the association between the immune response and the progression phenotype of COVID-19.

**Future plans:** This prospective cohort offers the possibility to study associations between immune response and progression phenotype according to age and gender as well as long-term immune response. In turn, we will be able to examine possible cumulative effects, taking into account several

clinical variables. The study is ongoing and we plan to extend it to increase the size of the cohort until 2024.

**Ethics and dissemination:** The study is approved by the Ethics Committee (IDIAPJGol ref 20/067-PCV IGTP ref COV20/00660 (PI-20-205). Dissemination will occur through presentations at National and International conferences and publications in international peer-reviewed journals.

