To date, seroprevalence studies conducted in Spain have used cross-sectional designs. Thus, they cannot provide systematic data on long-term antibody and cellular immune responses.

Thus, thorough serological and prospective studies are needed to determine whether ADE manifests among SARS-CoV-2 infections, either because of prior homologous infection or cross-reactive antibodies from other HCoVs. This will have particular relevance for vaccination plans.

Another interesting point that deserves further analysis is analyzing the different antibody specificities generated and their dynamics. Several studies have examined various types of antibodies identified against SARS-CoV-2 (Spike1, Spike2, Nucleocapsid, envelopes), identifying variable responses [8,9]. However, little is known about the simultaneous kinetics of the different antibodies over time. This can be analyzed with our cohort and also with the antigens used in the various vaccines that will be in the market in the next months. Thus, given the virus's short evolution, it is necessary to create an exhaustively monitored cohort. This cohort will make it possible to identify the kinetics of SARS-CoV-2-specific antibodies in individuals with different degrees of severity of COVID-19 and to know which levels of antibodies are protective against new possible reinfections in 3 years.

Crucially, this serological information will be used to strategically deploy HCW immune to the infection, limiting the risk of exposure and inadvertent propagation of the virus.

In conclusion, the present study is crucial to obtain epidemiological and clinical data to improve health policies for the prevention of SARS-CoV-2 infection. In addition, the study will be conducted simultaneously with the course of the pandemic, which will make it possible to obtain real-time data on the different waves that occur and, in turn, to study the SARS-CoV-2 endemic. Therefore, ProHEPIC-19 can be used as an ongoing platform to implement SARS-CoV-2 research projects with particular emphasis on incidence rate, reinfection, vaccines, and long term immune response.

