#### 6.2.1. SELECTION CRITERIA:

HCWs (physicians, nurses, auxiliars, COVID-19 researchers and other essential workers in direct contact with patients during the first, second or third wave of COVID-19) at risk of infection due to direct patient contact. Random sampling is being used for the inclusion of subjects. Different recruitment strategies are being applied to contact with participants such as email, phone calls.

Inclusion criteria:

≥ 18 years of age

Accept to take part in the study and sign the informed consent

To be a HCWs infected or exposed to SARS-CoV-2.

Exclusion criteria:

Not accepting taking part in the study and/or not to sign the informed consent

Not to be a HCW exposed to SARS-CoV-2

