### 6.3. STUDY PERIOD

From March, 31 2020 until recruitment is finished (estimated on June, 15 2021).

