## 6.6 VARIABLES MAIN COVARIABLES

- 1) Biological sex measured as a dichotomous variable in two categories (Male, Female)
- 2) Age (years): registered and analyzed as a continuous variable
- 3) Academic level: measured as a 5 levels variable (lower primary, completed primary, secondary, Post-secondary non-tertiary education, Short-cycle tertiary education, university).
- 4) Housing characteristics (meters, number of bedrooms, number of people in the same house, relationship, age of them)
- 5) Work variables (professional category, schedule, workplace's characteristics)
- 6) Clinical Spectrum of COVID-19 defined on procedure for action against cases of infection with the new SARS-CoV-2 coronavirus, defined according to national and international guidelines ( asymptomatic, Mild-Moderate Illness, severe-critical ) as defined in section 6.5
- 7) Clinical monitoring of COVID-19 symptoms, days of duration and monitoring Long Covid symptoms. (Table 3 , Table 4)
- 8) The date of symptom onset shall be considered as the date of appearance of the first symptoms. These symptoms, which are described in Table 2, are the confirmation of a positive RT-PCR test or antigen test (IgM (N) or IgG (N)).
- 9) Diagnostics. In the electronic medical records (EMR) for Primary Care and Hospitals, the diseases are codified using the International Classification of Diseases, version 10 (ICD-10), including the specific codes for COVID-19
- 10) Use of personal protective equipment (working and in the free time)
- 11) Medication prescribed. Classification number of drugs according to the Anatomical Therapeutic Chemical (ATC) Classification System.
- 12) Hospital admissions: admissions and emergency procedures according to the codes ICD-10 used in CMBD-HA.
- 13) Comorbidities: diabetes, hypertension, ischaemic heart diseases, other chronic comorbidities
- 14) Mortality by all causes. The initial data for the calculation of risk of death will be determined from March 15, 2020.
- 15) Psychosocial and healthy habits changes during pandemic (dream, eating, sexuality, physical activity and familiar relationship)
- 16) Laboratory Assays

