**Secondary Outcome Measures:**

4. Kinetics of SARS-CoV-2. IgM Nucleocapside

IgM (nucleocapside) ELISA kits (Inmunodiagnostic Limited ©). Positivity thresholds were provided by the assay manufacturers and were considered positive with an index value greater than 1.1, indeterminate from 0.9 to 1.1 and negative if <0.9 index units

[Time Frame: Baseline, 7 days, 15 days, 3, 6, 9 and 12 months after the beginning of the study]

5. Kinetics of SARS-CoV-2. IgG Nucleocapside

IgG (nucleocapside) ELISA kits (Inmunodiagnostic Limited ©). Positivity thresholds were provided by the assay manufacturers and were considered positive with an index value greater than 1.1, indeterminate from 0.9 to 1.1 and negative if <0.9 index units

[Time Frame: Baseline, 7 days, 15 days, 3, 6, 9 and 12 months after the beginning of the study]

6. Kinetics of SARS-CoV-2. IgG Spike

IgG (spike). ELISA kits DECOV1901 (Demeditec Diagnostics GmbH©). Positivity thresholds were provided by the assay manufacturers and were considered positive with an index value greater than 40, indeterminate from 32 to 40 and negative if <32 UI/ml

[Time Frame: Baseline, 7 days, 15 days, 3, 6, 9 and 12 months after the beginning of the study]

7. Kinetics of SARS-CoV-2. T-Cell

SARS-CoV-2 specific CD4+ and CD8+ T-cell responses we performed an IFN $\gamma$  ELISPOT assay. Wells will be considered positive if they contained at least 50 spot-forming cells per 10^6 PBMCs above the background level (2X mean + 3Xstandard deviation).

[Time Frame: Baseline, 7 days, 15 days, 3, 6, 9 and 12 months after the beginning of the study]

8. To assess the relation between clinical variables and initial RT-PCR results in the whole sample and by sex.

To study the differences between clinical spectrums and initial RT-PCR we will use ANOVAs or Kruskal-Wallis tests, after checking normality assumption using a Shapiro-test

[Time Frame: Baseline, to 12 months after the beginning of the study]

9. To analyse the relation between clinical variables and the interindividual differences in the immune response in early, mid, and long periods of immunization in the whole sample and by sex

To study the differences between clinical spectrums and immune response in early period we will use ANOVAs or Kruskal-Wallis tests, after checking normality assumption using a Shapiro-test . Similarly, to look for differences in antibody levels between sex, either a t-test or a Mann-Whitney test will be performed.

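### Cohorts recruited over about 14.5 months and several waves are compared with crude tests only, so an unequal wave mix can appear as a difference between cohorts

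*Combined protocol and SAP*

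**What the plan says.** Section 6.3 gives the study period as "From March, 31 2020 until recruitment is finished (estimated on June, 15 2021", and the Abstract adds: "The study is ongoing and we plan to extend it to increase the size of the cohort until 2024". Section 6.2.1 admits workers "in direct contact with patients during the first, second or third wave of COVID-19". Each cohort is filled to 675 by infection status (6.1, 6.5). Section 6.2.1 says that random sampling is used, but no section matches or balances the cohorts on date of entry.

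For the primary aim, 6.8.1 states: "Cohorts will be compared at each time point in terms of sociodemographic, epidemiological, clinical, and immunological information available". The method is that "an exploratory bivariate analysis will be performed using the tests of Chi Square, ANOVA, Kruskall-Wallis, depending on the application conditions assumptions". Section 6.8.2.2 links SARS-CoV-2 incidence to the collected covariables, and compares severity classes, with tests of the same kind. The smoothing and mixed-effects models in 6.8.2.1 split only by clinical spectrum or sex. Neither entry date nor wave is among the covariables in 6.6 or the necessary variables in Section 12, and no analysis uses them. The Background nevertheless says that the timing of the study makes it possible to "obtain real-time data on the different waves that occur".

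The visit schedule for the antibody outcomes is "Baseline, 7 days, 15 days, 3, 6, 9 and 12 months after the beginning of the study". Read literally, that is not time since each participant's entry.

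**The concern.** Cohort membership depends on infection, and infections come in waves. Two cohorts filled by infection status, without regard to date, may therefore have different calendar distributions. Several of the variables to be compared plausibly change with the calendar: contact with cases, use of protective equipment, symptoms, changes in habits and, at later visits, vaccination. One nominal visit can fall up to 441 days apart in calendar time for the first and last entrants, even before any extension.

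A crude comparison then mixes two things: whether infected and healthy workers differ, and when each group was recruited. A difference in protective equipment, for example, could be taken as a factor linked to infection when it reflects recruitment dates. The same applies across severity classes if their wave mix differs.

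**Working it through.** **The plan's own figure.** Section 6.4 gives 522 per group for a two-group F test with η² = 0.01, α = 0.05 and 90% power. With f² = 0.01/0.99 = 0.0101 and λ = 1044 × 0.0101 = 10.5, the noncentral F distribution gives 90.05% power at 522 per group. Inflation for 10% dropout gives 522/0.9 = 580. Both figures reproduce, and neither bears on this point. At 675 per cohort the power is 95.8%.

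**Entry window (6.3).** 31 March 2020 to 15 June 2021 is 441 days; 441/30.44 = 14.5 months.

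**Size of the possible distortion.** The documents give neither the wave mix of each cohort nor the level of any variable by wave, so both are assumed here. There are three entry periods. Within a period the prevalence of a characteristic is the same in both cohorts, so there is no true cohort difference. The formulas are:

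- spurious difference Δ = Σ (share of healthy − share of infected in the period) × prevalence in the period
- SE = √(2p(1−p)/675), with p the pooled prevalence
- chance of rejection ≈ Φ(|Δ|/SE − 1.96)

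Example with a 20-point difference in first-wave share (healthy 25/35/40%, infected 45/30/25%) and prevalence 30/50/70%:

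- healthy: 0.25×0.3 + 0.35×0.5 + 0.40×0.7 = 0.53
- infected: 0.45×0.3 + 0.30×0.5 + 0.25×0.7 = 0.46
- Δ = 0.07, SE = √(2×0.495×0.505/675) = 0.0272, |Δ|/SE = 2.57
- chance of rejection ≈ Φ(0.61) = 73%

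Results by simulation (4,000 runs per scenario, 675 per cohort, nominal 5%). The first figure in each pair is for prevalence 40/50/60%, the second for 30/50/70%:

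| Difference in first-wave share | Spurious difference (points) | Crude test rejects | Period-stratified test rejects |
|---|---|---|---|
| 0 (equal mix) | 0 / 0 | 4.0% / 5.2% | 4.4% / 5.5% |
| 10 points (30/35/35 v 40/30/30) | 1.5 / 3.0 | 8.9% / 19.8% | 5.5% / 5.4% |
| 20 points (25/35/40 v 45/30/25) | 3.5 / 7.0 | 24.5% / 72.6% | 5.0% / 5.0% |
| 40 points (20/30/50 v 60/25/15) | 7.5 / 15.0 | 79.0% / 100% | 4.7% / 5.1% |

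**Price of stratifying.** Effective n per cohort = 2 × 675 × Σ hᵢsᵢ/(hᵢ+sᵢ), where hᵢ and sᵢ are the healthy and infected shares in period i. This gives 668, 643 and 542 for differences of 10, 20 and 40 points. Power for η² = 0.01 is then 95.6%, 94.9% and 91.1%, against 95.8% unstratified. After 10% dropout (607 per cohort) it is 93.6%, 92.7% and 88.0%, against 93.8%.

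**The case against.** The strongest defence is that 6.8.1 serves an aim of building and describing a cohort, that its tests are labelled exploratory, and that crude description is legitimate for that purpose. This stands as far as the crude tables go, and they should stay. It does not cover inference. The Background calls it essential to identify factors associated with protection. Section 6.6.2 says the measurements will show prognostic roles and whether some variables act as confounders, and 6.8.2.2 ties incidence to the covariables. Crude bivariate tests cannot separate a confounder from a factor of interest.

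Three stronger readings are tempting, and the documents do not support them:

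- A reader might infer that wave differences are bound to appear as cohort differences. That needs both an unequal wave mix and a variable that changes between waves. Neither is documented, and with equal mix the distortion is zero.
- A reader might infer that infected workers enter at wave peaks. Section 6.5 also admits non-recent cases, with no stated upper limit on time since diagnosis, and classifies some workers as infected on antibodies alone, so infected workers can enter well after a wave. Both cohorts come from the same territory and prevention unit with stated random sampling. That bears on how large an imbalance may be, but does not guarantee balance on date.
- A reader might infer that the plan promises wave-specific results. The statement is in the Background; no objective or outcome is wave-specific.

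Section 6.5 also lists protective equipment and habits among the data taken at entry, while later visits record epidemiological data, symptoms and vaccinations. For the first two variables the issue therefore concerns mainly the baseline comparison.

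**Conclusion.** The gap is real: entry spans several waves, cohort membership depends on infection, and neither 6.8.1 nor 6.8.2.2 stratifies or adjusts for calendar period. The supportable conclusion is conditional. Calendar differences can appear as cohort or severity-class differences if the groups differ in wave mix. For assumed differences of 10 and 20 points in first-wave share, the crude 5% test at 675 per cohort rejects about 9–20% and 25–73% of the time with no true difference, against about 5% when stratified. These figures rest on assumed mixes and prevalences and show what is possible, not what has happened. Because the comparisons are exploratory, the harm is a misattributed association and not a failed confirmatory test. That the visits run from each participant's entry is itself an inference: it is the only workable reading for the 7- and 15-day visits, but the text does not say it.

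**What to change.** - In 6.5.1 and 6.6.2, state that visit times run from each participant's entry.
- In 6.6, add calendar period at entry, derived from the consent or first-visit date, with cut-points fixed in advance and used in all analyses. Entry date is not a listed variable, but the study should already hold it through consent and visit records.
- In 6.8.1, tabulate entry period by cohort. This shows directly whether the mix differs.
- In 6.8.1 and 6.8.2.2, keep the crude tables as description. Base inference on cohort and severity-class differences on period-stratified or period-adjusted tests: Cochran-Mantel-Haenszel for categorical variables, and linear or rank models with period as a factor for quantitative ones.
- For variables measured at follow-up, use the calendar period of the visit.

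The cost is plan wording and a modest amount of analysis, with little or no new data collection. Some precision is lost: very little for differences in mix of 10 or 20 points, and about 20% of effective sample size (542 of 675) at 40 points. The loss is larger where a period contains mostly one cohort, since a period with only one cohort adds nothing to a stratified test, or where severity classes are sparse within periods. Either situation should be reported.

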### 6.8.2. STATISTICS TO MEET SECONDARY AIMS

#### 6.8.2.1. TO DETERMINE THE KINETICS OF SARS-COV-2 ANTIBODIES AND CELLULAR IMMUNE RESPONSE IN EARLY, MID, AND LONG PERIODS OF IMMUNIZATION.

Two methods will be followed to study the kinetics of SARS-CoV-2 antibodies since symptoms onset. Locally Estimated Scatterplot Smoothing (LOESS) models will be fitted as a first descriptive approach. Then, nonlinear mixed-effects (NLME) models will be fitted to get the curves that would determine the kinetics.

##### LOCALLY ESTIMATED SCATTERPLOT SMOOTHING (LOESS) MODELS

LOESS models will fit as an initial descriptive manner of studying the antibodies, both IgM and IgG, evolution since diagnosis day. LOESS regression consists of fitting simple models (e.g., first or second degree polynomials) in subsets of data determined by a nearest neighbours algorithm. These LOESS curves will best stratified either per clinical condition or gender, and will be shown together with their 95% confidence interval (CI). We will use all the data available except for those from participants who never tested positive, grouping the data points per participant in the figures.

##### NONLINEAR MIXED-EFFECTS (NLME) MODELS

Mixed-effects models are generally useful when there are multiple measures per participant, as in this study. Random effects are included in the model to test if they may be causing any significant, and generally unexpected, significant influence in the modelling built by the fixed effects. Therefore, introducing random effects in the model help to control unobserved variance.

We will use NLME models to study possible differences in the dynamics (kinetics) of SARS-CoV-2 antibodies (IgM, IgG) levels since symptoms onset. After fitting a general model, the differences will be studied between clinical spectrums and biological sex, setting the largest group as reference groups for modelling. To fit these models, we will use all the data available except for those from participants who never tested positive. Time after diagnosis was discretized as follows: Tests made in the first 14 days since diagnosis are treated as "Day 15". Tests from days 15 to 29, as "Day 30", days 30 to 59 as "Day 60", days 60 to 89 as "Day 90", days 90 to 179 as "Day 180", days 180 to 269 as "Day 270", days 270 to 360 as "Day 360", and days 360 up to end of follow-up as "Day 450". However, antibody values beyond 450 days after diagnosis were not considered, as they were only available for 14 participants.

The general equations to be fitted will be:

$$IgM(t) = b_1 + (b_0 - b_1)e^{-k_1 t} - b_1 k_1 (e^{-k_1 t} - e^{-k_2 t})$$

$$IgG(t) = b_1 + (b_0 - b_1)e^{-k_1 t} - b_1 k_1 (e^{-k_1 t} - e^{-k_2 t})$$

Having  $t$  normalized per the maximum number of days (360). This general equation corresponds to an equation describing an exponential rise followed by an exponential decay.  $b_0$  corresponds to the baseline value,  $b_1$  corresponds to the asymptotic value (i.e., antibody levels at  $t \rightarrow \infty$ ),  $k_1$  corresponds to the rise rate, and  $k_2$  to the decay rate.

Nonlinear mixed-effects models will be built using the nlme package [14].

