## 5. HYPOTHESES AND OBJECTIVES

### 5.1 HYPOTHESES

The specific hypotheses are:

Infection with SARS-CoV-2 will produce different levels of immune response with respect to:

1. The kinetics and immune response is different depending on the clinical spectrum of COVID-19 disease.
2. The immune response is conditioned by age, sex and other clinical variables
3. Cytokines are good biomarkers to identify COVID-19 disease progression.

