#### 6.6.2. OUTCOME MEASURES

Outcome measures of immune response (SARS-CoV-2 Antibodies (N), cytokines, T-cells) and Covid-19 clinical symptoms will be measured at baseline and prospectively aiming to observe possible associations between possible prognostic factors and immune response. The baseline and prospective measurements will allow to assess their prognostic role and whether some of them appear as confounding factors.

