#### 6.8.2.2. TO ASSESS THE RELATION BETWEEN CLINICAL VARIABLES AND INITIAL RT-PCR RESULTS WITH THE INTERINDIVIDUAL DIFFERENCES IN THE IMMUNE RESPONSE IN EARLY, MID, AND LONG PERIODS OF IMMUNIZATION.

The incidence by SARS-CoV-2 will be linked to the sociodemographic, epidemiological, clinical and immunological information collected in the project. To analyze this, an exploratory bivariate analysis will be performed using the appropriate bivariate tests. Chi-squared tests will be used to find if there were any significant differences between the expected and the observed frequencies in categorical comparisons (e.g., the prevalence of symptoms per sex or clinical spectrum).. To study the differences between clinical spectrums and initial RT-PCR we will use ANOVAs or Kruskal-Wallis tests, after checking normality assumption using a Shapiro-test . Post-hoc analyses will be performed to find significant differences between clinical spectrum and immune response. Similarly, to look for differences in antibody levels between sex, either a t-test or a Mann-Whitney test will be performed.

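### No planned immune-response analysis includes age or comorbidity, so the severity contrast is unadjusted for them and the confounding assessment promised in 6.6.2 has no method

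*Combined protocol and SAP*

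**What the plan says.** Hypothesis 2 (Section 5.1) reads "The immune response is conditioned by age, sex and other clinical variables". Section 6.6 lists age as covariable 2, to be handled as continuous, and item 13 is "Comorbidities: diabetes, hypertension, ischaemic heart diseases, other chronic comorbidities". Section 6.6.2 then states that baseline and prospective measurement "will allow to assess their prognostic role and whether some of them appear as confounding factors".

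The immune-response analyses in Section 6.8.2 are these:

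- LOESS curves (6.8.2.1), "stratified either per clinical condition or gender".
- NLME models for IgM and IgG (6.8.2.1), where "the differences will be studied between clinical spectrums and biological sex", with the most numerous category serving for reference groups.
- Secondary aim 2 (6.8.2.2): bivariate tests. Clinical spectrum is compared by ANOVA or Kruskal-Wallis with post-hoc tests, and "to look for differences in antibody levels between sex, either a t-test or a Mann-Whitney test will be performed".
- Cytokines (6.8.2.3): t-test or Mann-Whitney for sex, ANOVA or Kruskal-Wallis for spectrum, at the 0.05 level.

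Outcome 9 in Section 6.6.2 relates clinical variables to immune response both overall and separately for each sex. The tests listed under it are again one for spectrum and another for sex.

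**The concern.** To judge whether a factor confounds an association, one compares the estimate with and without allowance for that factor, by stratifying or by modelling. The plan states this as an aim but specifies no such step for age or comorbidity. If severity classes differ in age or comorbidity, and these also affect antibody, T-cell or cytokine levels, the crude severity contrast mixes severity with them. Hypothesis 1 (response differs by clinical spectrum) and hypothesis 2 (response depends on age, sex and other variables) could then not be told apart. Secondary aims 2 and 3 rest on the same contrasts.

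**Working it through.** **Step 1: which factor enters which immune analysis.**

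| Analysis | Spectrum | Sex | Both together | Age | Comorbidity |
|---|---|---|---|---|---|
| LOESS | yes | yes | no (one or the other) | no | no |
| NLME | yes | yes | not stated | no | no |
| Aim 2 tests | yes | yes | no (separate tests) | no | no |
| Outcome 9 | yes | yes | by-sex analysis named, no combined estimate | no | no |
| Cytokines | yes | yes | no (separate tests) | no | no |

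The last two columns are empty throughout. The NLME random effects do not fill them: they model correlation within a person and do not remove confounding by measured differences between persons.

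**Step 2: the plan's own effect size.** Section 6.4 gives eta-squared 0.01, two groups, alpha 0.05 and 90% power. Then f² = 0.01/0.99 = 0.0101 and d = 2 × √0.0101 = 0.201 SD. The noncentral F gives power 0.9000 (just under 90%) at 521 per group and 0.9005 at 522, so the stated 522 reproduces. Dividing by 1 − 0.10 gives 580, as stated. No figure in the plan changes; 0.201 SD serves below only as a yardstick.

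**Step 3: bias from an omitted factor.** The documents give no confounder effect and no imbalance, so both are assumed. Bias = factor effect × prevalence gap between two severity classes.

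- 0.2 SD × 0.20 = 0.04 SD, or 20% of 0.201
- 0.2 SD × 0.30 = 0.06 SD, or 30%
- 0.5 SD × 0.20 = 0.10 SD, or 50%
- 0.5 SD × 0.30 = 0.15 SD, or 75%

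**Step 4: false positives when severity has no true effect.** SE = √(1/n₁ + 1/n₂) in SD units, and the rejection rate is P(|Z + bias/SE| > 1.96). The class sizes are also assumed: 200 + 407 = 607 is about 90% of 675 (675 × 0.90 = 607.5), and 68 + 607 = 675 puts about 10% in the smaller class.

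| Bias (SD) | 200 vs 407 (SE 0.0864) | 68 vs 607 (SE 0.1279) |
|---|---|---|
| 0.04 | 7.5% | 6.1% |
| 0.10 | 21% | 12% |
| 0.15 | 41% | 22% |

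**Step 5: does adjustment remove it?** A simulation of 4,000 replicates used 522 per group, a 0.5 SD factor, prevalence 20% versus 40% and no severity effect. The unadjusted contrast was significant in 35% of replicates. With the factor in a linear model, the figure was 5.0%.

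**The case against.** Several points on the other side are sound.

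- A reader might infer that everything is analysed one factor at a time. The NLME sentence does not support that: it names both spectrum and sex, with plural reference groups, and joint entry is compatible with it. This is an ambiguity to resolve.
- A reader might also infer that the severity contrast absorbs any sex imbalance. Outcome 9 is planned within each sex, and a comparison within one sex cannot be confounded by sex. What remains is that no combined estimate across the sexes is specified.
- The crude sex contrast is not wrong in itself. If severity lies on the path from sex to immune response, the crude contrast is the total effect of sex, which is a legitimate target.
- The bivariate work is called exploratory, LOESS is called descriptive, and a crude cytokine difference can be valid for a marker of disease type. This lowers the stakes, but Section 6.6.2 still states an aim about confounding that no listed analysis serves.
- The effect size in Section 6.4 is set for two groups of 522, in a design whose two cohorts are healthy and infected. It is not stated for the three severity classes, and the calculation above uses two classes where the plan tests three. The percentages are therefore illustrations.

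The future-plans part of the abstract speaks of taking several clinical variables into account, but gives no method. None of these points brings age or comorbidity into an immune-response analysis.

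**Conclusion.** The point holds in limited form. Followed as written, the plan gives severity contrasts unadjusted for age and comorbidity, so it cannot deliver the confounding assessment in Section 6.6.2 or separate hypothesis 1 from hypothesis 2. Sex is partly covered, and its place in the NLME is unclear.

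The size cannot be fixed from the documents. Under the assumed effects, imbalances and class sizes, bias is 0.04 to 0.15 SD and false positives run from about 6% to 41%. The documents do not show that such an imbalance exists; the finding is that the plan has no step to detect or remove one. This is a cheap improvement worth making to the secondary analyses.

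**What to change.** 1. For each antibody, T-cell and cytokine outcome, prespecify a linear or mixed model, on the log scale where needed, with clinical spectrum, age, sex and a single comorbidity term entered together. Report the crude and adjusted severity contrasts side by side; that comparison is the confounding assessment.
2. In the NLME section, state that spectrum and sex enter jointly, say which of b0, b1, k1 and k2 carry covariates, and add age and comorbidity where the model converges.
3. Report the sex contrast with and without severity, and say that the version without is the total effect if severity is a mediator.
4. Keep the bivariate tests and LOESS curves as description.

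The cost is SAP wording and extra model terms; the variables are already collected. The main downside is the NLME. Two spectrum terms plus one each for sex, age and comorbidity make 5, and on all four parameters 5 × 4 = 20 covariate coefficients, which may not converge. That is why the parameters carrying covariates should be named in advance. If the models are not wanted, the statement in Section 6.6.2 should be withdrawn.
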